5 PATIENT SELECTION CRITERIA

5.1 Inclusion Criteria

All male and female patients meeting these criteria:

1. Age \geq 18 years
2. PS ECOG 0-1
3. Histologically confirmed early breast carcinoma with positivity for hormone receptors (ER+ IHC >10%) and HER2 negative (IHC value 0-1+ and/or FISH not-amplified)

4. Primary resective surgery for early breast cancer with adequate assessment of lymph node status (sentinel lymph node biopsy or complete axillary dissection), with one of the following diagnostic stages:
T1-3, N0, M0
T1-3, pN1mic, M0
T1-3, pN1a, M0
5. Indication for adjuvant treatment with endocrine therapy (ET) or chemo-endocrine therapy (CET), according to the decision of the reference Breast Unit
6. Meeting the criteria for "intermediate" risk, i.e., no "low" or "high" risk of recurrence, as defined in the ministerial decree of 18/05/21:
 - Low risk defined by at least 5 of the following: G1, T1a-b, Ki67 < 15, N neg, ER > 80%
 - High risk, defined by at least 4 of the following: G3, T > 2, Ki67 > 30, N pos, ER < 30%
7. Indication for genomic test (Oncotype DX®, Mammaprint®, PAM50-Prosigna®, Breast Cancer Index®, EndoPredict®) by the Breast Unit
8. Ability to provide written informed consent to participate in the registry study, approved by the local Ethics Committee.
9. The patient underwent genomic testing starting from September 2021

5.2 Exclusion criteria

1. Low-risk and High-risk patients as defined in the Ministerial Decree of 18/05/21
2. ER negative and/or HER2 positive tumours
3. More than 3 lymph nodes involved at clinical/pathological staging
4. Invasive tumours <2mm evaluated by local pathologists
5. Previous history of breast cancer
6. Synchronous breast cancers
7. Multifocal tumours
8. Metastatic disease
9. Contraindications to adjuvant treatments
10. Performance status (PS ECOG) > 1 and / or other clinical factors that would make the patient a candidate and unsuitable for systemic adjuvant treatment or have received an exclusive indication for precautionary hormone therapy as part of the Breast Unit collegial assessment.
11. Psychiatric diagnosis that may affect the ability to participate in this study

6 STUDY DESIGN

The study is a retrospective and prospective, non-interventional, observational registry-based study that will enrol all patients with ER +/HER2-negative, T1-3 breast cancer with negative axillary lymph nodes or up to 3 positive axillary lymph nodes for whom Breast Units require genomic test to support adjuvant therapy decisions, according to current clinical practice.

Only patients who fulfill certain criteria specified in Ministerial Decree 18/05/2021 will be included unless otherwise agreed by the reference Breast Unit, in accordance with the specific diagnostic pathways activated by each site.

Data will be collected from September 2021 onwards. The tests are conducted as part of routine clinical care, independent of this observational clinical study.

The patient's baseline demographic characteristics, tumour clinicopathological features, pre and post-test therapeutic indication (CET vs ET), the test results, the actual adjuvant treatment received and time around data will be recorded in a dedicated registry.

7 VISITS

7.1 Schedule

Due to the observational nature of the study, no predetermined visit schedule can be planned, as patients performed visits at the clinic according to common clinical practice as programmed with the study physicians and staff.

Therefore, data from all assessments detailed in Section 7.2 will be collected if and where available at the study visits.

7.2 Assessments

The main data for this study will come from the medical records of each patient who participates. All information entered into the electronic Case Report Form (eCRF) should have corresponding documentation in the patients' medical records.

Throughout the observational period, data collection will adhere to standard clinical practices, whenever possible. This includes tests, procedures, and visits, which are conducted based on the usual clinical protocols at each site and at the discretion of the site physician.

Upon obtaining informed consent from the patients, the following data will be collected during the enrollment period, provided it is available:

- ✓ Enrollment and screening
 - General demography: sex, date of birth, age at the time of signing the consent, region of origin;
 - Menopausal state, previous surgery, previous therapies (including start and stop date, type of therapy).
 - Tumor characteristics: histology, grading, size of primary tumor, lymphnode status and number of metastatic lymphnodes, receptor status (ER, HER, PgR, Ki67)
 - Physical examination: weight, height, BMI
 - Prior and concomitant comorbidities and medication.
- ✓ Visit prior test
 - Therapy prior test
- ✓ Visit prior test
 - Test Type, test result, post therapeutic recommendation, patient decision
- ✓ End of study: specify reason

8 STATISTICAL CONSIDERATION

Although the true nature of this registry does not define apriori the number of patients ultimately expected, one of the main factors driving the sample size of this study is the clinical impact analysis and focuses on the accuracy of the estimate of the proportion of changes in planned adjuvant therapy pre and post genomic results.

8.1 Sample size

For the clinical impact analysis, 1000 patients, stratified in 60% of N0 and 40% of N1a patients, corresponding to 600 node-negative and 400 node-positive patients were enrolled.

After reaching the first 400 patients, an interim analysis is planned to check the accuracy of the assumed estimates and the feasibility of the study.

Moreover, to increase the accuracy of the results of this registry, enrolment and data collection will continue beyond the planned number of 1000 participants and will include all patients who meet the inclusion criteria throughout the whole study period.

8.2 Statistical analysis

It is assumed that the proportion of patients changing from chemotherapy (CT) followed by endocrine therapy (ET) to ET alone may be 50%, while the proportion of patients who change from ET to CT (followed by ET) is 10%. Therefore, the net change from CT to ET is expected to be 40%.

To demonstrate this expected impact in clinical practice, with a sample size of 1000 patients, the confidence intervals for these three estimates are expected to be 46.9%-53.1% (C.I. width of 6.2%) for changes from CT to ET; 8.3%-12.0% (C.I. width of 3.7%) for changes from ET to CT and 37.0%-43.1% (C.I. width of 6.1%) for the net change from CT to ET.

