1 BACKGROUND AND INTRODUCTION

Breast cancer (BC) is the most common cancer in women, with approximately 55,000 new diagnosed cases per year in Italy and 13,000 BC specific deaths. After BC surgery, adjuvant treatment with radiotherapy, endocrine therapy and chemotherapy in selected cases, represents the standard of care for hormone-positive (HR +), HER2-negative early breast cancer (eBC).

The choice of the type of adjuvant treatment generally takes into account the clinicopathological characteristics of the patient and the tumour, including age, menopausal status, tumour size, grading and Ki67 labelling index, number of lymph nodes involved and hormone receptor expression. These characteristics configure specific and different BC risk profiles and drive the individual adjuvant BC treatment as for recommended international guidelines.

However, some ambiguity still remains in the optimal adjuvant treatment in HR+/HER2- eBC, particularly regarding whether patients should receive or not adjuvant chemotherapy (CT) in addition to endocrine treatment (ET). Considering the absolute clinical benefit of adjuvant CT in addition to ET in HR + eBC with negative lymph nodes (N0) is modest (4% absolute recurrence risk reduction at 10 years), and considering that currently about 50% of patients with HR+/HER2- eBC still receive adjuvant CT, the proper patient selection for CT is a major clinical unmet need. The same applies to older patients (post-menopausal) with HR +/HER2- eBC with limited lymph node involvement (N1a), for whom the use of adjuvant CT is often associated with increase toxicity and avoidable side-effects.

Consequently, there is an urgent clinical need to support the optimal decision-making process for determining the best postoperative therapy, especially for "intermediate" risk patients for whom it is unclear whether they should receive endocrine therapy alone (ET) or chemotherapy (CT).

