In recent years, the role of molecular classifiers in prognosis and prediction has increased considerably. Indeed, several tests have been developed that assess the expression of panels of genes involved in the cellular replication of tumour cells and their metastatic ability, revealing specific genomic profiles associated with different risk of recurrence. Eventually, these tools can be used to refine the individual patients' prognosis and to estimate the benefit expected of adjuvant treatment. Accordingly, these tests provide critical support for therapeutic choice in patients with HR +/HER2- eBC (stage I-IIIA) at intermediate risk of recurrence according to clinical and histopathological factors, and help define whether adjuvant chemotherapy is appropriate in addition to endocrine therapy alone.

Several clinical trials have investigated the impact of these molecular classifiers on the choice of therapy. Multigenic tests have significantly changed the choice of treatment in a substantial proportion of patients, largely sparing the need for additional chemotherapy in favour of endocrine therapy alone.

Currently, some of these classifiers are available for routine clinical use in Italy, including OncotypeDX, Endopredict, Prosigna and Mammaprint. In line with the growing scientific evidence, the Ministry of Health, by decree of 18 May 2021, recognised the utility of genomic breast genomic tests and established their reimbursement according to some clinical criteria that can define the intermediate risk of recurrence, as derived from the scientific literature and the results of 3 prospective Italian experiences with the use of OncotypeDX.

The Ministry estimates that approximately 10,000 patients per year are expected to have access to the tests, resulting in a potential saving in chemotherapy prescription > 50% compared to what is currently proposed. Conversely, it is estimated that in about 10% of patients eligible for adjuvant endocrine therapy alone, the genomic test result will change the therapeutic approach and indicate the need to associate chemotherapy.

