4 ENDPOINTS

4.1 Co-primary endpoints

1. Establishment of a prospective Italian observational registry for the implementation of genomic tests in patients with HR +/HER2- breast cancer at intermediate risk of recurrence after the adoption of the Ministerial Decree of 18/05/2021
2. Measurement of the impact of genomic testing on adjuvant treatment choice (CET vs ET only) in terms of:
 - Rate of adjuvant treatment choice's change following the genomic test result (Breast Unit's pre-test vs post-test indication)
 - Saving in adjuvant chemotherapy compared to the pre-test indication
 - Addition of adjuvant chemotherapy to endocrine therapy alone compared to the pre-test indication
 - Type of adjuvant treatment the patient actually received

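### Section 8.2 uses all 1000 patients as the denominator for both the CT-to-ET (50%) and ET-to-CT (10%) rates, while Section 1 gives the matching figures on separate pre-test bases, and neither reading makes the section consistent

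*Protocol*

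**What the plan says.** Section 8.1 sets the size: "For the clinical impact analysis, 1000 patients, stratified in 60% of N0 and 40% of N1a patients". Section 8.2 assumes that "the proportion of patients changing from chemotherapy (CT) followed by endocrine therapy (ET) to ET alone may be 50" percent and that "the proportion of patients who change from ET to CT (followed by ET) is 10" percent, and subtracts the two to reach a net change of 40%. It continues: "with a sample size of 1000 patients, the confidence intervals for these three estimates are expected to be 46.9%-53.1% (C.I. width of 6.2" points) for CT to ET, 8.3%-12.0% (3.7 points) for ET to CT, and 37.0%-43.1% (6.1 points) for the net change. It names no denominator, no pre-test CET/ET split, no confidence level and no interval method.

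Section 1 reports the Ministry's expectations, and the same two figures appear there with a base attached. One is a "potential saving in chemotherapy prescription > 50% compared to what is currently proposed". The other is that "in about 10% of patients eligible for adjuvant endocrine therapy alone, the genomic test result will change the therapeutic approach". Section 4.1 lists among the co-primary components "Saving in adjuvant chemotherapy compared to the pre-test indication", and the addition of chemotherapy is likewise set against the pre-test indication.

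**The concern.** A patient's pre-test indication is either CET or ET alone. Only a CET patient can be spared chemotherapy, and only an ET patient can have it added. If the two rates are meant within those groups, as Section 1 words them, 1000 patients cannot supply 1000 to each rate, and two rates with different denominators cannot be subtracted to give a net change in patients.

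At stake is the only quantitative justification given for 1000 patients, and the meaning of the main co-primary measures. At a 50:50 split, the same data could be reported as 50% saved (of pre-test CET patients) or 25% saved (of all patients). Only the first is on the base that Section 1 uses for the Ministry's estimate. The interim look after 400 patients, which is meant to check the assumed estimates, also needs to know which base applies.

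**Working it through.** **Inputs.** n = 1000 (Section 8.1). Rates of 50%, 10% and net 40%, with their intervals (Section 8.2). Bases for the 50% and 10% (Section 1). Two-sided 95% confidence is assumed because it reproduces the figures. The pre-test CET share c is not given for this population, so it is assumed to be 50%, with a range of 30% to 70%.

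**Step 1: reproduce the stated intervals.** The Wilson limits are [p + z²/2n ± z√(p(1−p)/n + z²/4n²)] / (1 + z²/n), with z = 1.96.

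- 500/1000: 46.91-53.09 (stated 46.9-53.1)
- 100/1000: 8.29-12.02 (stated 8.3-12.0)
- 400/1000: 37.01-43.07 (stated 37.0-43.1)

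All six limits match. Agresti-Coull and Jeffreys intervals round to the same values; the Wald interval does not (8.1-11.9 for the 10% rate). Whichever of the matching methods was used, n was 1000 for every rate.

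**Step 2: rates conditional on the pre-test indication.** The CT-to-ET rate has 1000c patients and the ET-to-CT rate has 1000(1−c). The 95% Wilson intervals are:

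| Assumed CET share | CT to ET, 50% | Width (stated 6.2) | ET to CT, 10% | Width (stated 3.7) |
|---|---|---|---|---|
| 30% (300/700) | 44.4-55.6 | 11.2 | 8.0-12.4 | 4.5 |
| 50% (500/500) | 45.6-54.4 | 8.7 | 7.7-12.9 | 5.3 |
| 70% (700/300) | 46.3-53.7 | 7.4 | 7.1-13.9 | 6.8 |

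Each group is smaller than 1000 whenever both exist, so both intervals are wider than stated at any split. To obtain both stated widths would take 1000 CET patients plus 1000 ET patients.

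**Step 3: net and overall change on the same reading.** Write a = 0.5c and b = 0.1(1−c) as shares of all patients. The net change is a − b, with variance [a + b − (a − b)²]/n. The overall change rate is a + b.

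- c = 30%: net 0.15 − 0.07 = 8% (5.1-10.9); overall 22%
- c = 50%: net 0.25 − 0.05 = 20%; variance (0.30 − 0.04)/1000 = 0.00026; interval 16.8-23.2; overall 30% (Wilson 27.2-32.9)
- c = 70%: net 0.35 − 0.03 = 32% (28.7-35.3); overall 38%

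The net change is below 40% at all three shares.

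**Step 4: rates as shares of all 1000.** The first two intervals are then correct and 50 − 10 = 40 is a valid subtraction. But if 50% of all patients move from CET to ET, c must be at least 0.5, so the ET group is at most half of the total. The rate of change within it is 0.10/(1−c), which is at least 0.10/0.50 = 20%, against about 10% in Section 1. The overall change rate would be 50% + 10% = 60%. The net change is also a paired difference, with variance (0.5 + 0.1 − 0.4²)/1000 = 0.00044 and interval 35.9-44.1 (width 8.2), not 37.0-43.1 (width 6.1).

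**The case against.** The strongest reply is that Section 8.2 speaks of proportions of patients and subtracts one from the other, which presupposes a common denominator. On that reading the two component intervals are right. This stands: a reader might infer that the printed precision is simply wrong, but the loss of precision follows only on the conditional reading.

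A reader might also infer that, on the all-patient reading, every pre-test CET patient would have to drop chemotherapy (50% out of 50%). That borrows the Section 1 statement that "currently about 50% of patients with HR+/HER2- eBC still receive adjuvant CT". The statement describes treatment received across all HR+/HER2- early disease. This study excludes low-risk and high-risk patients and requires an indication for testing. At a 70% CET share the same reading needs 50/70 = 71% of CET patients to change, not all of them. The inference therefore fails. The bound of at least 20% among ET patients does not use that figure, and it holds.

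The link to the Ministry's figures is an inference too. Section 8.2 does not cite them, Section 1 says more than 50% rather than 50%, and a saving in prescriptions could be meant net of additions. The 10% is the figure whose conditional base is plain.

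Finally, this is a descriptive registry with no hypothesis test and no stated precision target. Enrolment continues beyond 1000, and detailed denominators for Section 4.1 may properly sit in the SAP. These points limit the harm. They do not reconcile figures that the protocol itself prints on conflicting bases.

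**Conclusion.** The point holds as a conflict of denominators between Sections 8.2 and 1. The use of n = 1000 for each rate is confirmed by reproducing the intervals. On the conditional reading, which the wording of Section 1 supports, both intervals are too narrow at every split (about 1.4 times too narrow at 50:50), and 40% is not a net change in patients. On the all-patient reading the two component intervals stand, but the ET-to-CT rate among ET patients is at least twice the Section 1 figure and the net-change interval is too narrow. No reading makes the whole section consistent.

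The size of the precision loss rests on an assumed pre-test CET share and on 95% Wilson intervals; its direction on the conditional reading does not depend on the share. This should be fixed, but it does not threaten the conduct of the registry.

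**What to change.** In Sections 8.2 and 4.1:

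- Define saving as CET-to-ET changes divided by patients with a pre-test CET indication, and addition as ET-to-CET changes divided by patients with a pre-test ET indication.
- Restate the two expected intervals on those denominators for assumed CET shares of 30%, 50% and 70%, and name the confidence level and interval method.
- Replace the 40% net change and its interval with a net change over all evaluable pre/post pairs, computed as a paired difference: 8%, 20% and 32% expected at the three shares, with 16.8%-23.2% at 50%. Leaving the 40% in place would keep the section inconsistent after the two rates are redefined.
- Give the overall change rate, the first component of the second co-primary endpoint, separately over all evaluable pairs: 30% (27.2%-32.9%) at 50:50.

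The cost is rewording. The stated precision and the expected net change become less favourable. No extra patients are needed, and no new data, since Section 6 already has the pre-test and post-test indications recorded.

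### The expected confidence interval for the net CT-to-ET change treats a difference of two opposite change rates as a single proportion (400 of 1000), and is too narrow on the protocol's own denominator

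*Protocol*

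**What the plan says.** Section 8.2 of the protocol assumes that "the proportion of patients changing from chemotherapy (CT) followed by endocrine therapy (ET) to ET alone may be 50"%, and that 10% change in the opposite direction. It then subtracts: "Therefore, the net change from CT to ET is expected to be 40"%.

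The precision statement follows: "with a sample size of 1000 patients, the confidence intervals for these three estimates are expected to be" 46.9% to 53.1% for CT to ET (width 6.2), 8.3% to 12.0% for ET to CT (width 3.7), and "37.0%-43.1% (C.I. width of 6.1%) for the net change from CT to ET". Neither the confidence level nor the interval method is named. The denominators of the 50% and 10% are not defined, and no share of patients with a pre-test CT indication is assumed.

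Section 8 says that "one of the main factors driving the sample size of this study is the clinical impact analysis". Section 8.1 plans an interim look after the first 400 patients to check the assumed estimates.

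Section 1 gives similar figures as ministry estimates: "a potential saving in chemotherapy prescription > 50% compared to what is currently proposed", and a change "in about 10% of patients eligible for adjuvant endocrine therapy alone, the genomic test result will change the therapeutic approach". There, each figure refers to one pre-test group, not to all patients.

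**The concern.** Each patient contributes +1 to the net change (CT to ET), −1 (ET to CT) or 0. The mean of such a score is not a binomial proportion. Its variance depends on how many patients move in total (here 60%), not only on the balance (40%). A one-sample interval for 40% ignores that and understates the uncertainty.

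The three intervals in section 8.2 are the only quantitative support the protocol gives for 1000 patients, and the interim look is meant to check the same assumptions. A reader would take from the protocol that the net change will be known to about ±3 points, and whoever does the check at 400 patients needs to know what the 50% and 10% are percentages of.

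**Working it through.** **Inputs.** From section 8.2: b = 0.50 (CT to ET), c = 0.10 (ET to CT), net = b − c = 0.40, n = 1000. Assumption: two-sided 95% intervals (z = 1.96), which reproduces all three printed intervals. The pre-test CT share s is not given and is varied.

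**Step 1: reproduce the printed figures.** One-sample Wilson intervals with n = 1000:

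| Events / n | Wilson 95% | Printed |
|---|---|---|
| 500/1000 | 46.91–53.09 | 46.9–53.1 |
| 100/1000 | 8.29–12.02 | 8.3–12.0 |
| 400/1000 | 37.01–43.07 | 37.0–43.1 |

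All three match. Agresti-Coull and Jeffreys intervals round to the same limits; Wald and Clopper-Pearson do not match all three. Each matching method is a one-sample method, so the 40% was handled as a simple proportion.

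**Step 2: both rates are shares of all 1000 patients.** This is the denominator behind the first two intervals.

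- Variance of the net change = (b + c − (b − c)²)/n = (0.50 + 0.10 − 0.16)/1000 = 0.44/1000, so SE = 0.0210.
- The one-sample variance is 0.40 × 0.60/1000 = 0.24/1000, so SE = 0.0155.
- 95% interval: 0.40 ± 1.96 × 0.02098 = **35.9% to 44.1%, width 8.2 points** (printed: 6.1).
- The Agresti-Min interval for a paired difference gives 35.8% to 44.0%, the same width.
- Patients needed for a width of 6.1: (2 × 1.96/0.061)² × 0.44 ≈ 1,817.
- Simulation (multinomial 0.5/0.1/0.4, n = 1000, 200,000 runs): SD of the net change 0.0209. A one-sample Clopper-Pearson interval on the net count, slightly wider than Wilson, covered 40% in about 85% of runs.

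This reading is possible only if s lies between 0.5 and 0.9, since 50% of all patients must start in CT and 10% in ET. At s = 0.5 every pre-test CT patient would have to switch (0.5/0.5 = 100%), and 20% of pre-test ET patients (0.1/0.5).

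**Step 3: the rates are within the pre-test CT and ET groups.** The net change over all patients is then 0.5s − 0.1(1 − s), with variance (0.5s + 0.1(1 − s) − net²)/n. The difference of the two group rates stays at 40%, with SE = √(0.25/(1000s) + 0.09/(1000(1 − s))). The component intervals are Wilson, on 1000s and 1000(1 − s) patients.

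| Assumed CT share s | Net change, all patients (95% CI) | Width | Width, difference of group rates | Width, CT to ET (printed 6.2) | Width, ET to CT (printed 3.7) |
|---|---|---|---|---|---|
| 0.3 | 8.0% (5.1–10.9) | 5.7 | 12.2 | 11.2 | 4.4 |
| 0.5 | 20.0% (16.8–23.2) | 6.3 | 10.2 | 8.7 | 5.3 |
| 0.7 | 32.0% (28.7–35.3) | 6.5 | 10.1 | 7.4 | 6.8 |

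The difference of group rates is never narrower than 9.9 points (best split s = 0.625). The net change over all patients equals 40% only at s = 5/6: 0.5 × 5/6 − 0.1 × 1/6 = 0.40.

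**Step 4: other attempts to recover 37.0–43.1.** Two independent rates with 1000 patients each give 36.4–43.6 (7.2); with 500 each, 34.9–45.1 (10.2). An 85% paired interval on all 1000 gives 37.0–43.0, but that level does not fit the other two intervals. No difference-based reading tested gives the printed limits.

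**The case against.** The best defence takes the rates as within-group and supposes that exactly five sixths of patients had a pre-test CT indication. The net change over all patients is then 40%, with an interval of 36.8% to 43.2% (random split) or 37.1% to 42.9% (fixed split), within about 0.2 points of the printed limits. This shows that the within-group reading need not contradict the 40%. It does not rescue section 8.2: no such share is stated, and the component intervals would then rest on about 833 and 167 patients, with widths of 6.8 and 9.2 against the printed 6.2 and 3.7.

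Three further points stand in part:

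- Under the within-group reading, the width for the net change over all patients (5.7 to 6.5 over the range tabulated) brackets the printed 6.1. What moves is the centre. The widths of 9.9 or more belong to a different quantity, the difference of two group rates.
- Section 8.2 does not cite the ministry estimates, so the within-group reading is an inference. Nor does section 1 supply the share: "currently about 50% of patients with HR+/HER2- eBC still receive adjuvant CT" describes treatment received by all such patients, not the pre-test indication in an intermediate-risk registry. A share of 50% is therefore only an assumption.
- The consequence is small. The study is descriptive, net change is not itself among the co-primary items in section 4.1, and section 8.1 lets enrolment run beyond 1000.

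None of this makes the printed interval right. An unseen statistical analysis plan would not cure it either, because the figure is printed in the protocol.

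**Conclusion.** The concern holds. The third interval is a one-sample interval for 400/1000 applied to a difference. On the denominator that the protocol itself uses for the other two intervals, it should be 35.9% to 44.1%: about 2 points wider in total, or about 1 point at each limit. If the rates are within-group, the first two intervals are too narrow as well, and the 40% is not the net change over all patients unless the CT share is five sixths. No single reading tested makes all three printed intervals correct.

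The miscalculation is certain, given the 95% level that reproduces all three figures. The replacement value is conditional on denominators the protocol does not state, and the within-group figures depend on an assumed CT share. The effect is confined to the stated planning precision; no power, type I error or decision rule changes. It should be corrected, but it does not threaten the study.

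**What to change.** In section 8.2, add one sentence giving the denominators of the 50% and 10%, and name the confidence level and interval method. Then:

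- **If both are shares of all 1000 patients:** replace the third interval with 35.9% to 44.1% (width 8.2 points, 95%, paired-difference variance). The first two intervals stand.
- **If they are rates within the pre-test CT and ET groups:** state the assumed pre-test CT share, say whether the net change means the change over all patients or the difference of the two group rates, and recompute the net change and all three intervals.

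Keep n = 1000. The cost is one or two sentences and one to three restated figures, with no extra patients and no change to design or data collection. The stated precision becomes less favourable, except that for a net change over all patients built from within-group rates it is mainly the expected value that moves.
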